3.1.2. Zavegepant PK Parameters

Zavegepant PK parameters from samples collected using Tasso and venous phlebotomy will be derived from the concentration-time profile using non-compartmental methods, as detailed in Table 2. Actual PK sampling times will be used in the derivation of PK parameters. In the case that actual PK sampling times are not available, nominal PK sampling time will be used in the derivation of PK parameters.

Table 2. Definitions of PK Parameters

Parameter	Definition	Method of Determination
C_{max}	Maximum plasma concentration	Observed directly from data
AUC_{last}	Area under the plasma concentration-time profile from time 0 to the time of the last quantifiable concentration (C_{last})	Linear/Log trapezoidal method
AUC_{inf}^a	Area under the plasma concentration-time profile from time 0 extrapolated to infinite time	$AUC_{last} + (C_{last}/k_{el})$, where C_{last} is the predicted plasma concentration at the last quantifiable time point estimated from the log-linear regression analysis
T_{max}	Time for C_{max}	Observed directly from data as time of first occurrence
$t_{1/2}^a$	Terminal half-life	$\log_2(2)/k_{el}$, where k_{el} is the terminal phase rate constant calculated by a linear regression of the log-linear concentration-time curve
CL/F^a	Apparent clearance	Dose/ AUC_{inf}
V_z/F^a	Apparent volume of distribution	Dose/($AUC_{inf} \times k_{el}$)

a. If data permits.

PK parameters from samples collected using Tasso-M20 will be adjusted for B/P ratio.

3.2. Secondary Endpoints

The secondary endpoints include the safety and tolerability of zavegepant as characterized by adverse events and clinical laboratory tests (discussed in Section 3.5).

3.3. Other Endpoint

The data collected for taste assessment using the sponsor-provided questionnaire will be numerically derived by measuring the length (using a scale with gradation of at least 0.1 centimeter) of the “x” marked by the participant relative to the “good trait.” For taste assessment, the data used in the analysis will be transcribed and rescaled to a score from 0 to 100 from the raw measurements on the Taste Assessment Questionnaire.

3.4. Baseline Variables

Baseline characteristics will be collected according to the SoA as specified in the protocol.

3.5. Safety Endpoints

The following data will be considered in standard safety summaries (see protocol for collection days, baseline assessment, and list of parameters):

- Adverse events (AE)
- Laboratory data

3.5.1. Adverse Events

An AE is any untoward medical occurrence in a patient or clinical study participant, temporally associated with the use of study intervention, whether or not considered related to the study intervention.

Any adverse events occurring following start of treatment will be considered as treatment emergent adverse event (TEAE). Events that occur during follow-up within the lag time of up to 37 days after the last dose of study intervention will be counted as treatment emergent. The time period for collecting AEs (“active collection period”) for each participant begins from the time the participant provides informed consent.

3.5.2. Laboratory Data

Safety laboratory tests will be performed as described in the protocol. To determine if there are any clinically significant laboratory abnormalities, the haematological, clinical chemistry (serum) and urinalysis safety tests will be assessed against the criteria specified in the sponsor reporting standards. The assessment will not take into account whether each participant’s baseline test result is within or outside the laboratory reference range for the particular laboratory parameter.

The baseline measurement is the predose measurement on Day -1.

4. ANALYSIS SETS (POPULATIONS FOR ANALYSIS)

Data for all participants will be assessed to determine if participants meet the criteria for inclusion in each analysis population prior to releasing the database and classifications will be documented per standard operating procedures.

Participant Analysis Set	Description
Enrolled	“Enrolled” means a participant’s, or their legally authorized representative’s, agreement to participate in a clinical study following completion of the informed consent process and assignment to study intervention. A participant will be considered enrolled if the informed consent is not withdrawn prior to participating in any study activity. Potential participants who are screened for the purpose of determining eligibility for the study, but do not participate in the study, are not considered enrolled, unless otherwise specified by the protocol.
PK Concentration Analysis Set	All enrolled participants who receive 1 single IN dose of zavegepan and provide at least 1 evaluable plasma concentration.
PK Parameter Analysis Set	All enrolled participants who receive 1 single IN dose of zavegepan and provide at least 1 evaluable PK parameters of interest.
Taste Assessment Set	All participants who receive at least 1 single IN dose of zavegepan and complete the Taste Assessment Questionnaire
Safety Analysis Set	All participants who take at least 1 dose of study intervention. Participants will be analyzed according to the product they actually receive.

5. GENERAL METHODOLOGY AND CONVENTIONS

Final analysis will be performed after study participant data set release following last participant last visit.

5.1. Hypotheses and Decision Rules

No statistical hypothesis will be tested in this study.

5.2. General Methods

5.2.1. Analyses for Binary/Categorical Endpoints

For binary or categorical variables, number of participants, numbers and percentages of participants meeting the categorical criteria will be presented in accordance with the Clinical Data Interchange Standards Consortium and Pfizer Standards (CaPS).

5.2.2. Analyses for Continuous Endpoints

For continuous variables, the data will be summarized using the number of participants, mean, median, standard deviation (SD), minimum, and maximum in accordance with the CaPS. For appropriate PK parameters, geometric mean and geometric coefficient of variation (%CV) will also be summarized.

5.3. Methods to Manage Missing Data

5.3.1. Pharmacokinetic Data

Methods to handle missing PK data are described below.

Concentrations Below the Limit of Quantification:

In all data presentations (except listings), concentrations below the limit of quantification (BLQ) will be set to zero. (In listings BLQ values will be reported as “<LLQ”, where LLQ will be replaced with the value for the lower limit of quantification.).

Deviations, Missing Concentrations and Anomalous Values:

In summary tables and plots of median profiles, statistics will be calculated having set concentrations to missing if one of the following cases is true:

1. A concentration has been collected as ND (ie, not done) or NS (ie, no sample).
2. A deviation in sampling time is of sufficient concern or a concentration has been flagged as anomalous by the pharmacokineticist.

Note that summary statistics will not be presented at a particular time point if more than 50% of the data are missing.

An anomalous concentration value is one that, after verification of bioanalytical validity, is grossly inconsistent with other concentration data from the same individual or from other participants. For example, a BLQ concentration that is between quantifiable values from the same dose is considered as anomalous. Anomalous concentration values may be excluded from PK analysis at the discretion of the PK analyst or pharmacokineticist.

PK Parameters:

Actual PK sampling times will be used in the derivation of PK parameters. If a PK parameter cannot be derived from a participant's concentration data, the parameter will be coded as NC (ie, not calculated). (Note that NC values will not be generated beyond the day that a participant discontinues). In summary tables, statistics will be calculated by setting NC values to missing; and statistics will be presented for a particular treatment with ≥ 3 evaluable measurements. PK parameter analyses will not be performed for a particular parameter if more than 50% of the data are NC.

If an individual participant has a known biased estimate of a PK parameter (due for example to an unexpected event such as vomiting before all the compound is adequately absorbed from the gastrointestinal tract), this will be footnoted in summary tables and will not be included in the calculation of summary statistics or statistical analyses.

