2.3.1. Risk Assessment

Potential Risk of Clinical Significance	Summary of Data/Rationale for Risk	Mitigation Strategy
Study Intervention Zavegeptan		
Hypersensitivity reactions	Hypersensitivity reactions including facial swelling and urticaria have occurred with zavegeptan.	Site staff and participants are instructed throughout protocol and ICD to immediately report all AEs post-dosing for further management instructions.
AEs associated with IN administration, such as dysgeusia, throat irritation, nasal congestion and nasal discomfort.	The potential risks are based on AEs reported in studies of zavegeptan IN administration, and the majority have been of mild to moderate intensity.	Eligibility criteria have been selected to ensure that only appropriate participants are included in the study (see Section 5.1). Nasal inspection will be conducted on Day -1 (to exclude participants with mucosal erythema, congestion, septal defects etc), and 24 h (\pm 30 min) postdose per the SoA. AEs and clinical laboratory results will be monitored on an ongoing basis.
Study Procedures		
The study intervention will be administered intranasally via a liquid spray device.	The IN administration could be affected by some human and operational factors, such as the way of handling the devices and the way of inhalation and exhalation. These may lead to higher variabilities in PK data.	Enhanced site training and participant education in terms of the study intervention administration. For all the study participants, all attempts would be made for study intervention administration performed by no more than 3 study staff members to minimize variability in device handling.
Relatively intensive PK sampling and narrow time window within 1 hour post dose.	Risk of PK sample collection outside the required time window might be higher.	Enhance site communication and training. Actual PK sampling times will be used in the derivation of PK parameters.
Other		
Atypical PK sampling methodology (Tasso devices)	Risk of improper collection procedure that could lead to compromised sample(s)	Enhanced site communication and training on Tasso device collection and handling procedures

PFIZER CONFIDENTIAL

CT02-GSOP Clinical Pharmacology Protocol Template (14 April 2023)

Page 30

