The correlations of paired Tasso-Plus versus venous phlebotomy concentrations and paired Tasso-M20 versus venous phlebotomy concentrations will be reported. Furthermore, Bland-Altman plot analysis will be performed for each pair to evaluate the bias and SD of the bias between the mean differences and to estimate an agreement interval within a 95% confidence limit.

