Appendix 1. Summary of Analyses

Endpoint	Population	Data Inclusion and Rules for Handling Intercurrent Events and Missing Data	Analysis Method
Zavegepant PK concentrations	PK Concentration Analysis Set	Observed and imputed (Section 5.3.1) data	Descriptive statistics
Zavegepant PK parameters	PK Parameter Analysis Set	Observed and imputed (Section 5.3.1) data	Descriptive statistics
Safety data	Safety Analysis Set	Observed and imputed (Section 5.3.2) data	Descriptive statistics
Taste assessment data	Taste Assessment Set	Observed data	Descriptive statistics

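### The anomalous-value rule in SAP 5.3.1 is not limited to one collection method, so a Tasso result could be excluded from the concordance analyses because it disagrees with its venous pair

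*SAP*

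**What the plan says.** **The rule.** SAP 5.3.1 defines the term: "An anomalous concentration value is one that, after verification of bioanalytical validity, is grossly inconsistent with other concentration data from the same individual". The sentence goes on to allow comparison with other participants as well. Two consequences follow.

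- In summary tables and median-profile plots, a value is set to missing if "a concentration has been flagged as anomalous by the pharmacokineticist".
- More broadly, "Anomalous concentration values may be excluded from PK analysis at the discretion of the PK analyst or pharmacokineticist".

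The only illustration is a within-profile one: "For example, a BLQ concentration that is between quantifiable values from the same dose is considered as anomalous". The section gives no numerical threshold. It does not limit the comparison to the same collection method, ask for the judgement to be made without sight of the paired value, or provide for a parallel analysis with the values kept.

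**The analyses it may reach.** SAP 6.1.1 states: "The correlations of paired Tasso-Plus versus venous phlebotomy concentrations and paired Tasso-M20 versus venous phlebotomy concentrations will be reported". It adds a Bland-Altman analysis ("Altman plot analysis will be performed for each pair to evaluate the bias and SD of the bias") with 95% limits. SAP 6.1.2 adds a mixed model for Tasso against venous AUC and Cmax. None of these carries its own data rule. SAP Appendix 1 gives the data rule for both PK endpoints as "Observed and imputed (Section 5.3.1) data".

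**The setting.** Protocol 8.5 has the Tasso and venous samples taken at the same time from the same participant. The study is open-label (Protocol 6.4). Protocol 2.3.1 lists compromised Tasso samples from faulty collection as a known risk.

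**The concern.** In a single-method PK study, an anomaly rule of this kind removes noise from a profile. Here the disagreement between two methods is the quantity to be estimated. The venous value is, on a plain reading, part of the same individual's other concentration data, so a large Tasso-venous gap can itself meet the definition.

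If pairs are removed because they disagree, the correlation rises and the limits of agreement narrow. If the discordance runs mainly in one direction, the estimated bias also moves towards zero. The study is meant to show concordance before Tasso sampling is used in children, and the SAP tests no hypothesis (5.1), so these estimates are the whole of the evidence.

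**Working it through.** **1. Does the text reach the concordance analyses?**

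| Text | Bearing on correlation and Bland-Altman |
|---|---|
| SAP 5.3.1, set-to-missing step | Names summary tables and median plots only; does not reach them |
| SAP 5.3.1, discretionary exclusion | Covers PK analysis, a term the SAP does not define |
| Protocol 9.3.2, Pharmacokinetic Analysis | Its subsection 9.3.2.2 contains the paired correlations, so that meaning is available |
| SAP 6.1.1 | Specifies both analyses, with no exemption from 5.3.1 |
| SAP Appendix 1 | Points both PK endpoints to 5.3.1, but lists the method only as descriptive statistics |

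Exclusion from the concordance analyses is therefore open to the analyst, but not prescribed.

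**2. The plan's own count.** 7 participants × 6 pairs = 42 per device (Protocol 9.5), which reproduces. The stated criterion is 30 to 40 data points. 42 − 40 = 2 pairs (4.8%) could go with 40 left, and 42 − 30 = 12 pairs (28.6%) with 30 left. Meeting the count would not reveal selective exclusion.

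**3. Possible size.** The following are assumptions, not in the documents: ordinary Tasso/venous log-ratio SD s = 0.15, no true bias, and k = 2 of n = 42 Tasso values at one third of the venous value. The ratio scale is also a choice, because the SAP does not name the Bland-Altman scale.

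All pairs kept:

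- Mean log-ratio = −k·ln 3/n = −2 × 1.0986/42 = −0.0523, a ratio of 0.95.
- Variance = s² + k(1 − k/n)(ln 3)²/(n − 1) = 0.0225 + 2 × 0.9524 × 1.2069/41 = 0.0786, so SD = 0.280.
- Limits = exp(−0.0523 ± 1.96 × 0.280) = 0.55 to 1.64.

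Both discordant pairs removed: exp(±1.96 × 0.15) = 0.75 to 1.34, ratio 1.00.

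The result depends on the fold-difference treated as gross. Simulation under the same assumptions, excluding every pair beyond the cut-off, gives:

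| Cut-off | Pairs removed, on average | Limits after exclusion |
|---|---|---|
| none | 0 | 0.55-1.64 |
| about 1.7-fold (exp(0.8 ln 2) = 1.74) | 2 | 0.75-1.34 |
| 3-fold | 1 | 0.65-1.47 |
| 5-fold | 0 | 0.55-1.64 |

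If the two values are at one half instead, limits of 0.64-1.46 become about 0.74-1.35 at 1.7-fold and are essentially unchanged at 3-fold.

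**4. Correlation.** Adding an assumed between-participant log-SD of 0.5 and the protocol's half-life of about 3 hours, removing both one-third pairs moves r on the log scale from 0.968 to 0.991. The effect on the geometric mean ratios of SAP 6.1.2 was not computed.

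**The case against.** The best defence is that the rule is about profile shape. Its only example is a BLQ result between quantifiable values, the mandatory step touches only summary tables and median plots, and the wider exclusion is optional. Nothing in the SAP mentions checking a Tasso value against its venous pair. All of that is correct. A reader might infer that the SAP instructs the analyst to delete discordant Tasso results, and the documents do not support that reading. What remains is that the wording does not confine the comparison to one method, and nothing shields the paired analyses.

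A second defence is visibility. SAP 6.1.1 lists all concentrations and plots each participant with every collection method together, and Protocol 8.5 requires handling deviations to be documented. This makes unnoticed removal less likely. It does not correct a reported correlation or limit of agreement, and no tabulation of exclusions with reasons is called for.

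Third, bioanalytical validity is not the same as a good sample: a correct assay of a badly collected sample is still compromised. That also stands, and it is why documented collection and handling failures should remain grounds for exclusion.

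Finally, no hypothesis is tested and no acceptance limit is set, so no formal conclusion can be reversed. The harm is to the estimates.

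**Conclusion.** The point holds as a gap in the wording. SAP 5.3.1 allows a bioanalytically verified Tasso value to be left out because it disagrees with its venous pair, and 6.1.1 does not prevent this. Exclusion chosen in that way would bias the concordance results towards agreement.

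The size cannot be fixed from the documents. The SD, the number and depth of discordant pairs and the cut-off are all assumed, and the simulation excludes every pair beyond the cut-off although the SAP says only that such values may be excluded. The move from 0.55-1.64 to 0.75-1.34 is what a strict cut-off would produce. With a 5-fold cut-off there is no effect.

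It is also tempting to add that a paediatric study without venous samples could not recognise such values, so that the reported agreement would be out of reach there. The documents do not support this. They do not give the paediatric sampling scheme, and the SAP's own example, an isolated BLQ, can be seen in a Tasso profile alone.

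**What to change.** Amend SAP 5.3.1 and 6.1.1 as follows.

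- **Quantifiable values.** For the Tasso-venous correlation and Bland-Altman analyses, exclude a value only for a collection, handling or assay failure documented without reference to the paired concentration.
- **BLQ values.** Report pairs with a BLQ member by device. Keep them at zero in any analysis of untransformed differences, as 5.3.1 already provides. Count them separately from any log-ratio analysis, because zero has no logarithm.
- **Mixed model.** Derive the AUC and Cmax for the Tasso-venous comparison in 6.1.2 from the same retained concentrations.
- **Sensitivity.** Show the results with the current anomaly exclusions as a labelled sensitivity analysis.
- **Reporting.** Tabulate exclusions with reasons by device.

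The cost is SAP wording, derivation of the Tasso-venous AUC and Cmax from the retained concentrations, one sensitivity run and one table. No further participants, samples or visits are needed. The downside is that the reported limits of agreement may be wider.

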5.3.2. Safety Data

For the analysis of safety endpoints, the standard rules for imputation according to CaPS will be applied.

6. ANALYSES AND SUMMARIES

6.1. Primary Endpoints

6.1.1. Zavegepan PK Concentrations

The plasma concentrations and plasma equivalent concentrations (derived from Tasso-M20 samples) of zavegepan will be listed and descriptively summarized by nominal PK sampling time, for each collection method (Tasso-Plus, Tasso-M20 and venous phlebotomy), and by race (non-Japanese and Japanese), as data permit for the PK Concentration Analysis Set. Individual participant and summary profiles (mean and median plots) of the plasma concentration-time data will be plotted by collection method and race using actual and nominal times, respectively. Mean and median zavegepan plasma concentration profiles will be presented on both linear and semi-log scales.

Presentations for zavegepan plasma concentrations will include:

- A listing of all concentrations sorted by participant ID, collection method, race and nominal time postdose. The concentration listing will also include the actual times. Deviations from the nominal time will be provided in a separate listing.
- A summary of concentrations by collection method and by race, and nominal time postdose, where the set of statistics will include n, mean, median, SD, %CV, minimum, maximum and the number of concentrations above the LLQ.
- Median concentrations time plots (on both linear and semi-log scales) against nominal time postdose by collection method and by race (all collection methods on the same plot per scale (similarly for race), based on the summary of concentrations by collection method, race and time postdose).
- Mean concentrations time plots (on both linear and semi-log scales) against nominal time postdose by collection method and race (all collection methods on the same plot per scale (similarly for race), based on the summary of concentrations by collection method, race and time postdose).
- Individual concentration time plots by collection method and by race (on both linear and semi-log scales) against actual time postdose (there will be separate spaghetti plots for each collection method and race per scale).
- Individual concentration time plots by participant (on both linear and semi-log scales) against actual time postdose [there will be separate plots for each participant (containing all collection methods and all race) per scale].

The correlations of paired Tasso-Plus versus venous phlebotomy concentrations and paired Tasso-M20 versus venous phlebotomy concentrations will be reported. Furthermore, Bland-Altman plot analysis will be performed for each pair to evaluate the bias and SD of the bias between the mean differences and to estimate an agreement interval within a 95% confidence limit.

6.1.2. Zavegepant PK Parameters

The PK parameters of zavegepant will be listed and summarized descriptively for each collection method (Tasso-Plus, Tasso-M20 and venous phlebotomy), and by race (non-Japanese and Japanese), as data permits for the PK Parameter Analysis Set. Each zavegepant PK parameter will be summarized including the set of summary statistics as specified in Table 3.

For AUC_{last} , AUC_{inf} , and C_{max} , box and whisker plots for individual participant parameters will be constructed for each collection method and overlaid with geometric means.

Table 3. PK Parameters to be Summarized Descriptively by Collection Method and Race

Parameter	Summary Statistics
AUC_{inf} , AUC_{last} , C_{max} , CL/F , V_z/F	N, arithmetic mean, median, SD, %CV, minimum, maximum, geometric mean and geometric %CV
T_{max} , T_{last}	N, median, minimum, maximum
$t_{1/2}$	N, arithmetic mean, median, SD, %CV, minimum, maximum

Supporting data from the estimation of $t_{1/2}$ and AUC_{inf} will be listed by collection method and by race: terminal phase rate constant (k_{el}); goodness of fit statistic from the log-linear regression (r^2); the percent of AUC_{inf} based on extrapolation ($AUC_{extrap}\%$); and the first, last, and number of time points used in the estimation of k_{el} . This data may be included in the clinical study report.

For the Tasso vs. Venous comparison, natural log-transformed zavegepant AUC_{inf} (if data permit), AUC_{last} and C_{max} will be analyzed using a mixed effect model with blood collection method as fixed effect and participant as random effect. Estimates of the adjusted mean differences (Test – Reference) and corresponding 90% CIs will be obtained from the model with Venous as the Reference group and Tasso-M20 (or Tasso-Plus) as the Test group. The adjusted mean differences and 90% CIs for the differences will be exponentiated to estimate the adjusted geometric means ratio (Test/Reference) and 90% CIs for the ratios.

For race comparison, natural log-transformed zavegepant AUC_{inf} (if data permit), AUC_{last} and C_{max} will be analyzed using an ANOVA model with race as fixed effect. Estimates of the adjusted mean differences (Test – Reference) and corresponding 90% CIs will be obtained from the model with non-Japanese as the Reference group and Japanese as the Test group. The adjusted mean differences and 90% CIs for the differences will be exponentiated to estimate the adjusted geometric means ratio (Test/Reference) and 90% CIs for the ratios.

